**Table 3: Proposed Study Measures**

**A. Screening Measures**

10-item Short Portable Mental Status Questionnaire (Kahn et al., 1960)	
 
• Screens for moderate-to-severe cognitive impairment
 
• Good reliability and validity (Kane and Kane, 1981)
 
• Ineligible if answer more than three items incorrectly
 

Physical examination of joints and muscles by study rheumatologist	
 
• Determines clinical presence of OA in LE joints
 
• Rates functional significance using ACR arthritis functional class (Hochberg et al., American College of Rheumatology, 1992)
 

History of falls	
 
• Self-reported number of falls in last 2 years (Mobility and aging survey developed and used by the Centers for Disease Control and Prevention Healthy Aging Network).
 

B. Dependent Measures: Assessed at baseline, 2, 6, 12 and 18 months	
Primary Proximal Outcomes	
National Cancer Institute (NCI) Percent Energy from Fat Screener (Thompson et al., 1998)	
 
• Assesses usual daily intake from fat over previous 12 months
 
• Correlates strongly with true dietary intake (Thompson et al., 2007)
 

NCI Fruit and Vegetable Screener (Thompson et al., 2000)	
 
• Obtains fruit and vegetable intake during a typical day
 
• Correlates strongly with true dietary intake (Thompson, 2002)
 

Block Brief Food Frequency Questionnaire (FFQ) (Block et al., 1990)	
 
• Assesses 6-month changes in energy intake, % energy from fat, saturated fat, grams of fiber, servings of fruit and vegetables based on 70 food items
 
• Reliability and validity demonstrated in a wide range of age, gender, income and ethnic groups including low-income women (Coates et al., 1991; Block et al., 1992; Lanza et al., 2001; French et al., 2000)
 

Primary Distal Outcomes	
Weight and BMI	
 
• Weight measured without shoes using same calibrated Tanita BWB-800 digital scale
 
• Height measured without shoes to calculate BMI using Seca 214 portable stadiometer
 

4-position Balance Stand	
 
• These 4-positions are the most sensitive balance stands taken from the Berg balance scale, a valid and reliable measure of balance in older adults.
 

Timed Up and Go Test (TUG)	
 
• Measures the amount of time it takes to stand up from a seated position, walk 3 meters, turn around, walk 3 meters back to the chair, and sit down. Validity and reliability of the instrument have been demonstrated in populations of older adults with and without physical impairments (Steffen et al., 2002; van Hedel, Wirz, & Dietz, 2005)
 

Physical Activity Scale for the Elderly (PASE)	
 
• Measures self-reported occupational, household, and leisure activities for individuals 65 years of age and older
 
• Can be administered by telephone, mail, or in person
 
• PASE scores are calculated from weights and frequency values for each of the types of activities
 

Waist Circumference	
 
• Assesses body composition change due to exercise
 
• Measured using Gulick 150 centimeter anthropometric tape
 

Western Ontario and McMasters University Osteoarthritis Index (WOMAC) (Bellamy et al., 1989)	
 
• Measures LE function using pain, stiffness, and physical function subscales
 
• Cronbach's as of 0.81, 0.74, and 0.95, respectively ([name] et al., 2010)
 
• Will enable us to compare our findings to ADAPT trial
 

Functional Lower Extremity Muscle Strength (Guralnik et al., 1995)	
 
• Functionally assesses LE muscle strength and endurance
 
• Measures time to complete five full stands from sitting position
 
• Correlates well with age and with knee flexor and extensor muscle strength (Csuka and McCarty, 1985)
 

6-minute Walk Test (Guyatt, et al., 1985)	
 
• Measures functional exercise capacity reliably; correlates moderately to strongly with treadmill or bicycle ergometer tests
 
• Number of feet walked in 6 minutes measured by Rolatape Measure Master
 
• Used in ADAPT and recommended by Whitham and Avenell (2010) for future diet trials with older adults
 

Arthritis Impact Measurement Scales for elderly respondents (GeriAIMS) ([name] et al., 1991)	
 
• Measures arthritis-specific symptoms of depression, anxiety, and combined depression/anxiety
 
• Cronbach's as of 0.73 for depression, 0.72 for anxiety, and 0.82 for combined depression/anxiety ([name] et al., 2010)
 

California Older Adult Stroop Test (COAST) (Pachana, Thompson, Marcopolos, & Yoash-Gantz, 2004)	
 
• Modeled from the traditional Stroop test, the California Older Adult Stroop Test (COAST) was developed specifically for use in a geriatric population and requires participants to distinguish between words and colors.
 

Speed of Processing, Selective Attention, and Divided Attention (UFOV Test) (Edwards, Vance, Wadley, Cissell, Roenker, & Ball, 2005).	
 
• These three domains are measured using the valid and reliable computer-based Useful Field of View (UFOV) test. Participants' speed of processing and visual attention abilities are measured through three increasingly difficult tasks of stimulus detection, divided attention, and selective attention
 

Task Switching (Connections Test) (Salthouse et al, 2000)	
 
Modeled from the classic Trail Making Test, the purpose of the Connections Test is to draw a line connecting an alternating sequence of letters and numbers randomly placed on a page. Time taken to complete this task is measured
 

Working Memory (Digit Span) (Cooper, Sagar, Jorda, Harvey, & Sullivan, 1991; Wilson, 2002)	
 
Digit Span forward and backward (Weschler, 1987) and digit ordering
 

Attention (SDMT)	
 
Symbol digit modalities test (Smith, 1982) and digit symbol substitution (Wechsler Adult Intelligence Scale—Revised. Psychological Corporation; San Antonio, TX: 1981) will be used to measure working memory, visuomotor coordination, and selective attention are important factors that determine the final score.
 

California Verbal Learning Test (CVLT)	
 
Test-retest reliability of CVLT in healthy adults are supported (Woods, Delis, Scott, Kramer, Holdnack, 2006)
 
Measures total learning, delayed recall, intrusion errors, and recognition performance (Lacritz, Cullum, Weiner, & Rosenberg, 2001)
 

Blood Pressure	
 
Blood pressure will be assessed using the NHANES protocol.
 

C. Independent Variables	
Demographic variables	
 
Age, race/ethnicity, sex, income, marital status, living arrangements, employment status, type of health insurance coverage, and education
 

Chronic Conditions	
 
Witham and Avenell (2010) recommend that future diet trials with older adults assess presence of co-morbid conditions
 
Will use index of co-morbid conditions used in GeriAIMS study ([name] et al., 1991)
 
Inquires about presence of 14 separate conditions and measures extent to which each condition interferes with activities
 

**Exploratory Variables**—The following measures will explore longitudinal risk of seeking total joint replacement, health care utilization, health care costs, and quality of life and technology usage in this population prior to and following participation.

**Readiness for Joint Replacement Surgery.** We will create a measure that will assess 1) degree of interest in total hip and knee replacement surgery and 2) intent to use either procedure in the next 6 months. We will monitor movement on that measure over time.

**Health Care Utilization.** Participants will complete the Health Care Utilization Measure (Lorig et al., 1996). to report number of physician and ER visits, hospital stays, hospital days, surgeries, outpatient tests and procedures, and medications used. We will obtain permission from participants to use their Social Security numbers to request healthcare utilization data from the Centers for Medicare and Medicaid. We will obtain data encompassing hospital and outpatient use, conditions, and prescription drug use. Specifically, we will request the MedPAR ss/ls/snf, Beneficiary Summary File, the Beneficiary Annual Summary file, and the corresponding crosswalk files for calendar years **2011-2016**. Calendar year data will be converted to **36**-month periods that correspond to **12** months prior to and **-18** months following baseline for each participant. Drs. [name] and [name] have prior experience analyzing these data ([name] et al., 2000; [name] et al., 2003).

**Health-Related Quality of Life.** The EQ-5D assesses 5 dimensions of health-related quality-of-life: mobility, self-care, usual activities, pain/discomfort, and anxiety/depression (EuroQoL, 1990). Respondents rate each dimension on 3 levels: no problems, some problems, extreme problems. The EQ-5D can be used to translate scores into Quality-Adjusted Life Years (QALYs) for cost analyses. **Witham and Avenell (2010) also recommend the inclusion of these measures in future diet trials with older adults.**

**Technology Usage:** Participants will complete questions regarding technology use during the baseline outcomes assessment. We are trying to assess if they have internet access and if they utilize it to search for health or medical information online. We will obtain this information from the participants during their baseline outcome assessments. We would like to provide health-related website links for their reference during the program and maintenance period. In addition, it will allow us to create future projects related to health information and technology use.

**Blood Pressure:** Blood pressure will be assessed using the NHANES protocol. Readings will be obtained at baseline, 2, 6, 12, and 18 month follow-up visits. Participants with blood pressure over 180/110 mm Hg or below 90/50 mm Hg will be asked to contact their physician immediately after the reading and ask for instructions for care. If the participant's physician cannot be reached then an ambulance will be called for the participant. Participants with readings in these ranges will not be eligible to participate in the study.

**Mediators**—We will measure variables related to self-efficacy, social support, intrinsic motivation, and barriers to weight loss as outlined in Table 4 at all timepoints.

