Conceptual Model—We have used Social Cognitive Theory (SCT) (Bandura , 1982; Bandura 1989) and Self Determination Theory (SDT) (Deci and Ryan 1991; Deci and Ryan 1980; Deci and Ryan, 1985) to guide model development, intervention design, and selection of study measures. SCT specifies that behavior change occurs as a result of the dynamic interaction between modifications in behavior, cognition (self-efficacy, perception of barriers), and the environment (social support), and that modeling and reinforcement can be used to encourage change. SDT is a broad-based theory of human motivation (Ryan and Deci , 2000) that is increasingly cited to explain how personal or intrinsic motivation can lead to increased physical activity and improved eating patterns (Deci and Ryan, 1985). According to SDT, an individual's increased intrinsic motivation to improve eating and activity patterns should positively relate to self-efficacy and the ability to overcome barriers and solicit support.

**Figure 1.** Conceptual Model for Proposed Fit and Strong! vs. Fit and Strong! Plus Comparison Study

Our Conceptual Model (Figure 1) shows that demographic, disease, and arthritis functional class variables are antecedents that will be controlled in multivariate analyses. These antecedent variables predispose some participants to be more responsive to both the PA and PA/diet interventions. SE/motivation for exercise and SE/motivation for dietary behaviors are expected to change as a result of exposure to treatment. They are also expected to mediate the impact of the interventions. ***Both the dietary change and PA interventions tested will use social modeling, exercise logs or food diaries, individualized goal setting, and shared group problem solving to increase mastery and goal achievement in small incremental steps to enhance self regulatory skills. We hypothesize that customary Fit and Strong! will increase SE and intrinsic motivation for exercise only; whereas Fit and Strong! Plus will increase SE and motivation for both exercise and weight loss. These mediators will impact the interim primary outcome of physical activity and dietary behaviors. These improved behaviors, in turn, are hypothesized to impact the more distal primary outcomes of exercise maintenance and weight loss along with the associated secondary outcomes shown.***

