will be repeated 4 times at 3 sites to achieve a final targeted baseline sample of 400 participants (i.e., 2 interventions x 3 sites x 4 replications x 17 participants = 408 participants). Outcome measures will be obtained at baseline, 2, 6, 12 and 18 months (see Figure 2, Projected Consort Flow Diagram, Appendix C).

**Settings**—We will partner with the Chicago Park District and Westside Health Authority (WHA) to conduct the trial. Although we require 3 sites to conduct the trial, the Park District has identified 4 sites that can participate, and WHA has identified 1 site. The Park sites include Smith Park (Northwest), Wicker Park (Northwest), Washington Park (Southeast), and Columbus Park (Southwest), and the WHA site includes their location on the westside (see more information about the sites in Appendix D). **All sites are staffed by nationally certified exercise instructors who will be trained separately to conduct either customary Fit and Strong! or Fit and Strong! Plus. (See letters from [name], CEO, Chicago Park District from [name], CEO, National Recreation and Park Association, and from [name], CEO, Westside Health Authority in Section 14).**

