**Fit and Strong! Plus.** In addition to the activities described above for the health education component of the customary program, Fit and Strong! Plus also addresses SE for diet behaviors and **includes techniques to achieve a minimum 5% weight loss (see Instructor Manual, Appendix F). The goal is to increase consumption of fruits and vegetables, decrease percent energy from saturated fats, decrease consumption of sugar sweetened drinks, and reduce overall caloric consumption such that participants will achieve a minimum 5% weight loss at 6 months that will be maintained over time—the same dietary goals achieved by the ORBIT trial.** To boost SE for diet, we ask participants at baseline to specify dietary and weight outcomes that they plan to achieve through participation in Fit and Strong! Plus. Week 1 addresses the relationship between OA, obesity, and disability, and stresses the importance of a 5% decrease in weight. The instructor lets participants know that the remainder of the program will provide the tools that will help them achieve this goal. **During Week 1, all participants receive The Calorie King Calorie, Fat, and Carbohydrate Counter ([www.CalorieKing.com](http://www.CalorieKing.com)) that lists calories and fat contained in popular foods. Participants are taught how to use the book to fill out food diaries in which they record all food consumed during Week Two. Participants bring the food diaries to class where their content is discussed during classes 5, 6 and 7. The diary documents all food eaten daily, including portion size, time of day, where and with whom food was eaten, other activities while eating, and mood. Participants calculate the number of pounds that they need to lose over the next 6 months to achieve a minimum 5% weight loss. Participants who weigh <= 250 lbs. are asked to adhere to 1200-1500 calories per day and persons who weigh more than 250 lbs. are asked to adhere to 1500-1800 calories per day. All participants are urged to consume foods that contain no more than 3 grams of fat per serving. Participants are encouraged to maintain the diary on their own after Week 2 and are given diaries to maintain at graduation from the class in session 24. Weight is measured weekly on a scale that remains at the study site.** Food diaries and routine weigh-ins help participants track progress over time, increasing awareness of dietary habits and motivating participants to modify habits to meet goals.

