**Table 5. RE-AIM Process Evaluation Framework for Fit and Strong and Fit and Strong Plus**

Reach (participation)	Implementation (dose and fidelity)

 
• # of participants completing Fit and Strong! sessions
 
• # of participants completing Fit and Strong! Plus sessions
 
• Age, education, race/ethnicity of participants
 
• % of eligibles in site catchment area (census data)
 
	
 
• Attendance
 
• Instructor attrition
 
• Site visit evaluations in Week 4 using systematic checklist
 
• Instructor listserv and hotline staffed by PIs and dietitian
 
• Participant/Instructor program evaluations (Appendix I)
 

Efficacy Changes at 2 and 6 months in mediators, dietary, weight loss, and OA symptom change outcomes	Maintenance • Maintenance of change at 12 and 18 months in mediators, dietary, weight loss, and OA symptom change outcomes Follow-up interviews with participants, instructors and Park District managers to assess sustainability
Adoption • Perceived barriers to implementing Fit and Strong Plus • # of participants in Fit and Strong Plus using weight loss maintenance strategies (e.g., self-monitoring, problem solving, stimulus control, regular physical activity) – subset of questions in Diet TR calls	

**Data Management**—All survey forms will be designed using REDCap. Project staff will enter data into REDCap during data collection, and data will be automatically uploaded for processing. Data will be stored in univariate form. We will use Stata's "reshape" command to reformat to multivariate form if necessary. We will run standard checks for outliers, duplicates, and other errors common to complex data entry and processing. All missing data will be flagged, and we will develop routines for imputations of missing data where the proportion of missing data is small. More complex imputation strategies will be developed if warranted. All data files will be password protected, and hard copies of questionnaires will be stored in locked cabinets in the research office.

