where  $Y_{it}$  represents a particular outcome variable for person  $i$  at time  $t$ , *Plus* is a dummy variable for the Fit and Strong! Plus effect, relative to customary Fit and Strong!, *Plus\*Time* represents the interaction with time, *ARA* is a covariate,  $u_i$  is the random effect for person  $i$  and  $e_{it}$  is a person-time specific error term. The *Plus\*Time* interaction tells us whether the rate of change with respect to time is greater (or less) in the Plus condition compared to customary Fit and Strong!. As shown, the model is for a continuous outcome, but it can be estimated for a wide variety of outcome variables (e.g., logistic regression and ordered logistic regression models). Time can be represented in multiple ways in addition to the simple linear effect shown here. By including the square of time we can test whether the effects of time are non-linear, and by including properly coded dummy variables for discrete time, we can test more specific hypotheses regarding non-linear effects. A crucial assumption of such models is that the person-specific error term,  $u_i$ , is uncorrelated with the remaining variables, which is plausible given the randomized design. The model, as written, assumes an “exchangeable” correlation matrix among the errors. However that assumption can be relaxed by using simple auto-regressive or Toeplitz (banded) correlation structures. All analyses will be done using Stata.

Analyses of secondary outcomes will examine the magnitude of between and within group differences at all time points to determine whether the addition of a diet component to Fit and Strong! benefits these outcomes (as expected) or is neutral or harmful with respect to certain outcomes. Exploratory analyses will evaluate movement on the new readiness for total joint replacement measure, and will examine patterns and trends in healthcare utilization, healthcare cost, and quality of life between and within the two study groups.

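### The fat screener's stated 12-month recall reaches back before the program at the 2- and 6-month visits, so if respondents follow it, a true arm difference in fat intake is diluted at the visits named for dietary efficacy

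*Combined protocol and SAP*

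**What the plan says.** Table 3 places the fat screener under Primary Proximal Outcomes, with the NCI fruit and vegetable screener and the Block Brief Food Frequency Questionnaire (FFQ). Its description reads "Assesses usual daily intake from fat over previous 12 months". The heading over the block is "Dependent Measures: Assessed at baseline, 2, 6, 12 and 18 months", and the Approach section agrees: "Outcome measures will be obtained at baseline, 2, 6, 12 and 18 months".

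Table 5, the process-evaluation framework, defines efficacy as "Changes at 2 and 6 months in mediators, dietary, weight loss, and OA symptom change outcomes" and maintenance as "Maintenance of change at 12 and 18 months in mediators, dietary, weight loss, and OA symptom change outcomes".

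The Conceptual Model puts diet ahead of weight loss in the causal chain: "These mediators will impact the interim primary outcome of physical activity and dietary behaviors". The description of the Plus curriculum aims to "reduce overall caloric consumption such that participants will achieve a minimum 5% weight loss at 6 months that will be maintained over time", and also sets goals for less saturated fat and less fat per serving. The plan therefore expects diet to have changed by 6 months.

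The Data Analysis section uses the Plus-by-Time interaction to learn "whether the rate of change with respect to time is greater (or less) in the Plus condition compared to customary Fit and Strong". It also allows a squared time term or dummy variables for discrete time.

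The other two dietary measures have different frames. The fruit and vegetable screener asks about a typical day. The Block FFQ also yields percent energy from fat, but its entry mentions six-month changes without saying whether six months is a recall window or only an interval between readings.

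**The concern.** A measure that looks back 12 months cannot fully register a change that began 2 or 6 months ago. At those visits part of each answer describes diet before the program, which randomization makes alike in the two arms on average. That shared part shrinks any real difference between them.

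Fat intake is a target of the Plus arm, and dietary behavior is the step that is meant to explain weight loss. A weak early reading could be taken as failure of that step when it only reflects the recall window. As the pre-program months drop out of the window, the score can also move between visits while true intake is flat. Table 5 would label such movement at 12 months as maintenance.

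**Working it through.** **Inputs from the documents.** Recall window W = 12 months (Table 3). Visits at 0, 2, 6, 12 and 18 months (Table 3 and Approach). Program length 8 weeks, taken as 2 months (Completed Work). The plan gives no figure of its own on this point to reproduce.

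**Assumptions.** The program starts at baseline; a later start would raise the pre-program share. How respondents average over the window is not in the documents, so a range is used: even averaging, or exponential weights that favour recent diet with half-life h = 1, 3 or 6 months, cut off at 12 months.

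**Step 1. Pre-program share of the window** = max(0, 12 − m)/12 at visit m.
- 2 months: 10/12 = 83%
- 6 months: 6/12 = 50%
- 12 and 18 months: 0%

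**Step 2. Share of a true arm difference that is read.**
- Immediate sustained change, even averaging: min(m, 12)/12.
- Immediate sustained change, recency weights, m ≤ 12: (1 − 2^(−m/h))/(1 − 2^(−12/h)). For example, h = 6 and m = 2 gives 0.206/0.750 = 0.275; h = 1 and m = 6 gives 0.9844/0.9998 = 0.985.
- Change building linearly over months 0 to 2, even averaging: the build-up contributes 1 month-equivalent, so (1 + (m − 2))/12 for m from 2 to 12. This gives 1/12, 5/12 and 11/12.

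| Assumption | 2 mo | 6 mo | 12 mo | 18 mo |
|---|---|---|---|---|
| Immediate, even averaging | 0.167 | 0.500 | 1 | 1 |
| Immediate, half-life 6 | 0.275 | 0.667 | 1 | 1 |
| Immediate, half-life 3 | 0.395 | 0.800 | 1 | 1 |
| Immediate, half-life 1 | 0.750 | 0.985 | 1 | 1 |
| Builds over 2 months, even averaging | 0.083 | 0.417 | 0.917 | 1 |

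If the true difference is zero throughout, every entry multiplies zero, so no false difference appears.

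**Step 3. Linear slope.** The mean visit time is 7.6 and the sum of squared deviations is 219.2, so the balanced random-intercept slope is Σ(t − 7.6)y/219.2. For an immediate constant effect of 1 unit:
- Perfect measure, y = (0, 1, 1, 1, 1): 7.6/219.2 = 0.0347 per month.
- Even 12-month average, y = (0, 0.167, 0.5, 1, 1): 13.07/219.2 = 0.0596.
- Recency weights: 0.0412 (half-life 1) to 0.0556 (half-life 6).

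The window therefore adds 0.0065 to 0.0249. The larger part, 0.0347, arises from fitting a straight line even to a perfect measure.

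**Step 4. Discrete time.** The 12-minus-6-month contrast for the same flat effect is truly 0. It would read 1 − 0.500 = 0.50 with even averaging, and 0.015 to 0.333 with recency weights.

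**Step 5. Relapse just after month 6.** The 12-month score would still read 0.50 with even averaging, or 0.015 to 0.333 with recency weights, when the truth is 0. The 18-month score covers months 6 to 18 and reads 0, correctly.

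**Step 6. Block FFQ, if its recall is 6 months.** The pre-program share is 4/6 = 67% at 2 months and 0% at 6 months. With even averaging it reads 33% and 100% of an immediate change, or 1/6 = 17% and 5/6 = 83% of one that builds over the program.

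**The case against.** The strongest reply is that the size of the problem rests on how people answer. The only source for the window is one descriptive line in Table 3; the administered form is not in the documents. If respondents mostly report recent diet, the screener reads about 98% of the true change at 6 months and little is lost. This stands, and it is why the conclusion is conditional and given as a range. Even that most favourable case reads only 75% at 2 months.

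Second, Table 5 is a process-evaluation table and says only that dietary outcomes are read at 2 and 6 months. It does not name this screener. The Block FFQ covers energy intake and saturated fat, so it is closer to the stated 6-month goals. This also stands in part. But the screener is a listed primary proximal outcome collected at those visits, and nothing in the available text limits where it is interpreted. Two stretches of the Approach section, before the Conceptual Model and before the visit schedule, were not available to check.

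Third, the slope argument is mostly about linear time rather than recall, and the Data Analysis section already offers discrete time. That is correct. A reader might infer from the 0.0596 figure that the recall window creates the apparent growth; Step 3 shows that 0.0347 of it is present without any recall problem. Discrete time removes the slope problem but leaves the dilution at 2 and 6 months.

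**Conclusion.** The concern holds conditionally. If respondents follow the recall window that Table 3 states, a true arm difference in fat intake is diluted at 2 and 6 months. The overlap fractions, 10/12 and 6/12, follow directly from the documents. The loss at 2 months is clear: 25% to 83% for an immediate change, and 92% if change builds over the program with even averaging. The loss at 6 months runs from about 2% to 50%, or 58% in the gradual case. These sizes rest on assumed averaging patterns and on the program starting at baseline.

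Three stronger readings are tempting and not supported. A reader might infer that early change is certainly understated, or that the score will visibly rise between 6 and 12 months. With a 1-month half-life that rise is about 0.02 of the effect, and the documents do not settle how respondents average. A reader might infer that the trial's main result is at risk. Weight is measured directly, the sample size is built on weight, and dilution produces no false difference under the null. A reader might also infer that the screener should be dropped. Its 18-month window holds no pre-program time, so it remains usable there.

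This is an inexpensive improvement to the reading of one primary proximal measure.

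**What to change.** In the analysis plan:
- Do not use the fat screener's 2- and 6-month values as efficacy readings. Report them descriptively, with the 10/12 and 6/12 overlap stated.
- Analyse the screener with the discrete-time coding that the Data Analysis section already allows, not with a linear Plus-by-Time slope.
- Base its between-arm conclusion on 18 months (window months 6 to 18), and label the 12-month value as the average over months 0 to 12.
- Report the fruit and vegetable screener at 2 months as its own outcome if wanted, not as a stand-in for fat intake.

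In Table 3, state the Block FFQ's recall period. If it is 6 months or shorter, take percent energy from fat at 6 months from that instrument.

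The cost is a few sentences and one table line, with no new visits, forms or participants. The price is that this screener gives no early efficacy estimate. There would also be no clean percent-fat reading at 2 months unless the Block recall is 2 months or shorter, and none at 6 months if that recall exceeds 6 months.
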